2.2.2 Secondary endpoints

1-2 Polyp characterization using white light according to CONECCT classification Polyp characterization using NBI according to CONECCT classification Polyp characterization using standard histology according to CONECCT classification

3- Evaluation of the degree of certainty of characterization after examination by: strong or weak

4- Endoscopist seniority: junior or senior: <2000 vs \ge 2000 colonoscopies performed.

5- Polyp size defined on NBI examination: 1-5mm vs 6-9mm vs 10-20mm

3. Study population

3.1 Description of the population

- Any adult patient having a colonoscopy scheduled in one of the participating hospitals.

The expected number of patients is around 690, with the aim of characterizing at least 690 polyps. The average number of polyps per patient is estimated at between 1 and 2. A limit of 4 polyps per patient will be set for data collection. Data collected for the study should relate to the first 4 polyps removed.

3.2 Pre-inclusion criteria

- Patients over 18 having a colonoscopy scheduled in one of the participating hospitals (CHD Vendée and CHU de Nantes).

- Patient having agreed to participate in the study and having given express consent

- Patient affiliated with or benefiting from a social security system

3.3 Inclusion criteria

• Patients with 1 or more polyps smaller than 20mm observed during colonoscopy

3.4 Non-inclusion criteria

- Patient undergoing emergency colonoscopy for ongoing GI bleeding or occlusion symptoms
- Patients with chronic inflammatory bowel disease (IBD): UC, Crohn's disease or unclassified colitis
- Patients with familial adenomatous polyposis
- Pregnant or breast-feeding women
- Minor patient
- Patients under guardianship or deprived of their liberty
- Patient unable to understand protocol and/or give express consent
- Patient not affiliated to a social security system or beneficiary of such a system
- · Patients hospitalized or treated without their consent

4. Conduct of the study

4.1 General research methodology

The research has the following characteristics:

- Type of research: Interventional research with minimal risks and constraints (Study of electronic staining techniques (also known as 'virtual chromoscopy') during colonoscopy, without the addition of contrast media or specific intervention).
- Bicentric study: CHD Vendée, CHU de Nantes
- Prospective study

4.2 Study and analysis techniques

4.2.1 Detailed description of evaluation parameters

Parameters assessed :

• Characterization of polyps, using different analysis techniques: conventional adenomatous versus typical hyperplastic or scalloped adenomatous.

4.2.2 Description of techniques and analyses

Study diagram :

- All endoscopists participating in the study will receive an initial one-hour training course in NBI polyp characterization, delivered by an expert endoscopist in image analysis ([name] [name], graduate of the DIU 'Endoscopie Diagnostique Avancée').
- A verification test (rate of correct answers >95%) will be carried out before each operator is authorized to take part in the study, based on an independent set of images of 30 colonic polyps.
- Each patient corresponding to the pre-inclusion criteria and agreeing to take part in the study is "pre-included". During colonoscopy, the presence of any polyp(s) smaller than 20mm is determined. The right colon, which is the preferred site for adenomatous scalloped polyps, will be examined with particular attention by a second pass under white light. This 2^{ème} pass is routinely performed in standard practice, for example to check fast-moving areas during colonoscopy, and will only increase examination time by around 2-3 minutes. Patients without a polyp smaller than 20 mm are not included in the study.

- Each polyp measuring less than 20mm will be analyzed in white light and NBI, as follows:
- 1) White-light image analysis

2) Switch to NBI mode by simply pressing the 'NBI' button on the endoscope handle (immediate acquisition of the NBI image with photographic recording in LB and NBI). A prediction of the histological type of polyp according to the CONECCT classification is made by the endoscopist and noted in the CRF, together with the degree of certainty (strong or weak).

The study is limited to 4 polyps per patient. Only data from the first 4 polyps removed will therefore be collected.

- All polyps detected and analyzed by NBI are then removed by excision (forceps excision, mucosectomy) according to the usual procedure and analyzed by conventional histology (gold standard).
- If it is impossible to characterize a polyp by NBI (image of poor quality or diagnosis impossible), the examination will be considered a technical failure of NBI, but the polyp will be removed for histological analysis in accordance with current recommendations.
- If the polyp is not recovered for histological analysis, or if interpretation is impossible (coagulation artifacts after standard resection, for example), the examination will be considered a technical failure of standard histology.
- Anatomopathology departments will be involved and will collaborate between the 2 centers to ensure standardized interpretation of polypectomy specimens.

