From an anatomopathological point of view, the situation has become relatively complex in recent years, with the description of new colonic polyp entities (8). Historically, only conventional adenomatous polyps (at risk of degeneration) and typical hyperplastic polyps (without risk of degeneration) were distinguished, which explains why endoscopic classifications have focused on the ability to distinguish these 2 anatomopathological entities. The new WHO anatomopathological classification describes scalloped polyps, which it subdivides into 4 different morphological entities constituting evolutionary lesion spectra. The histological appearance of these lesions distinguishes between 1) typical hyperplastic polyps (reclassified as non-adenomatous scalloped lesions, and accounting for some 80-90% of scalloped lesions overall), 2) sessile scalloped adenomas/polyps, 3) sessile scalloped adenomas with dysplasia, and 4) traditional scalloped adenomas. While typical hyperplastic polyps have virtually no degenerative potential, other scalloped (adenomatous) lesions may degenerate. Descriptively, typical hyperplastic polyps are generally small and occur throughout the colon. Sessile scalloped polyps/adenomas do not show cytological lesions of dysplasia in the basal state. They are essentially characterized by abnormalities in the maturation of colonic crypt cells. They share many morphological features with hyperplastic polyps of the microvesicular subtype, in particular their predominantly right-sided location. They are generally larger than hyperplastic polyps. Foci of dysplasia identical to that of "classic" adenomas may appear in sessile scalloped polyps/adenomas. Sessile scalloped lesions with dysplasia are thought to progress more rapidly to adenocarcinoma than classical adenomas of equivalent dysplasia grade. Traditional scalloped adenomas are different from sessile scalloped lesions. They generally appear in the left colon and rectum, and are of villeinous or filiform architecture. They are characterized by the presence of a dysplasia rich in cells with penicillate eosinophilic cytoplasm and ectopic crypts not anchored to the

muscularis mucosa. Many of them are associated with a classic adenomatous component, and their evolutionary kinetics are identical to those of classic adenomas.

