2.1 Objective and primary endpoint

2.1.1 Primary objective

To evaluate the diagnostic performance of the NBI for the characterization of scalloped colonic polyps of all types [typical hyperplastic and adenomatous scalloped; i.e. CONECCT IH and CONECCT IS] versus conventional adenomatous [i.e. CONECCT IIA] during colonoscopy in a population of "non-expert" endoscopists.

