2.1.2 Primary endpoint

Sensitivity of NBI compared with histological analysis (=reference method). Number of polyps characterized as scalloped (CONECCT IS) on reading by NBI compared with the number of polyps characterized as scalloped on standard histology.

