5.1 Study data collection and processing

5.1.1 Data collection

An electronic case report form (eCRF) will be created for each patient. All information required by the protocol must be provided in the eCRF. It must include the data needed to confirm compliance with the protocol and all the data required for statistical analysis, and to detect major deviations from the protocol.

Data will initially be collected on paper in an observation notebook, with a form for each polyp visualized, filled in by the endoscopist.

All data are then entered into the eCRF by investigators, clinical study coordinators (CECs) or clinical research nurses (CRNs).

The people responsible for filling in the eCRF (investigator, CEC, IRC, etc.) must be identified and their responsibilities defined in each center's table of delegated responsibilities (kept in the investigator binder).

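### No stated rule keeps the endoscopist's call from the pathologist or fixes how histology becomes a CONECCT class, so NBI sensitivity may be biased upward by an unknown amount

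*Combined protocol and SAP*

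**What the plan says.** Section 2.1.2 makes histology the reference for NBI sensitivity. Under section 4.2.2 the endoscopist predicts the histological type in CONECCT terms before excision and notes it in the CRF. The polyp is then removed by the usual procedure and sent for conventional histology. Section 4.4 lists the white-light and NBI predictions among source data held outside the medical record.

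On how pathology is to read the specimens, section 4.2.2 says only this: "Anatomopathology departments will be involved and will collaborate between the 2 centers to ensure standardized interpretation of polypectomy specimens". No section mentions blinding of pathologists, the content of the specimen request, or central or double reading.

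Section 2.2.2 lists as an endpoint "Polyp characterization using standard histology according to CONECCT classification". Section 2.1.1 gives the labels a histological meaning: "typical hyperplastic and adenomatous scalloped; i.e. CONECCT IH and CONECCT IS". No conversion table is given and no one is named to apply it.

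**The concern.** A sensitivity estimate is sound only if the reference is read independently of the test. Here the test result exists before the specimen leaves the endoscopy room, and no rule governs what travels with it. Standardized interpretation between two departments makes readings consistent; it does not make them independent of the optical call.

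The risk is greatest where the histology is close. Section 1.1 says of sessile scalloped lesions: "They share many morphological features with hyperplastic polyps of the microvesicular subtype". Section 2.1.2 and the primary analysis in 5.2.1 name IS as the target, and 2.2.1 asks for IS characterization within scalloped polyps, so both lean on that boundary.

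The conversion step is a second opening. Section 1.1 describes four WHO scalloped types, while CONECCT offers IH and IS. Sections 1.1 and 2.1.1 read together place the adenomatous scalloped types in IS. However, Figure 3 labels IS as sessile, and section 1.1 says that traditional scalloped adenomas differ from sessile lesions and often carry a conventional adenoma component. Whether they go to IS or IIA is left to judgement, and that choice matters even for IH+IS versus IIA.

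If the call is borrowed, both kinds of disagreement move toward agreement, so sensitivity and specificity rise together. If it is the NBI call that is borrowed, the McNemar comparison with white light in 5.2.1 would tilt toward NBI. Recruiting more polyps would not shrink this bias.

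**Working it through.** **Inputs from 5.2.1:** 690 polyps; 5% not analysable; mix IIA 50%, IH 40%, IS 10%; sensitivity 90%; stated precision ±3%.

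**1. The plan's own figure.** Analysable polyps: 690 × 0.95 = 655.5. Half-width = 1.96 × √(s(1−s)/n).
- IH+IS: n = 655.5 × 0.50 = 327.75; 1.96 × √(0.09/327.75) = 3.25 points. This rounds to the stated 3.
- IS only: n = 655.5 × 0.10 = 65.55; 1.96 × √(0.09/65.55) = 7.26 points at 90%, and 1.96 × √(0.16/65.55) = 9.68 points at 80%.

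So ±3 belongs to IH+IS. A bias in IS sensitivity has to be set against about 7 to 10 points.

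**2. IS as target, borrowing between IH and IS.** IS = 65.55 and IH = 655.5 × 0.40 = 262.2. Two inputs are assumptions, since the documents give neither: 10% of IH are called IS by NBI (26.22 polyps), and a share f of discordant IH/IS readings follows the NBI call.

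Observed sensitivity = (IS·s + f·26.22) / (IS·s + f·26.22 + IS·(1−s)·(1−f))

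| True s | f | Numbers | Observed |
|---|---|---|---|
| 90% | 0.10 | 61.62 / (61.62 + 5.90) | 91.3% |
| 90% | 0.25 | 65.55 / (65.55 + 4.92) | 93.0% |
| 80% | 0.10 | 55.06 / (55.06 + 11.80) | 82.4% |
| 80% | 0.25 | 59.00 / (59.00 + 9.83) | 85.7% |

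At f = 0 there is no bias.

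**3. IH+IS versus IIA.** An IH/IS swap stays inside the scalloped group, so it changes nothing here. Borrowing across the scalloped/IIA line would. Let b be the share of discordant polyps recoded to the NBI call, with prevalence 50% and specificity 80–90% (b and specificity are assumptions). Then TP′ = TP + b·FP, FN′ = (1−b)·FN, and observed sensitivity = TP′/(TP′+FN′). For example, with sensitivity and specificity both 90% and b = 0.20: TP′ = 0.45 + 0.20 × 0.05 = 0.46; FN′ = 0.80 × 0.05 = 0.04; 0.46/0.50 = 92.0%.

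| True s | b = 10% | b = 20% | b = 50% |
|---|---|---|---|
| 90% | 91.0–91.1% | 92.0–92.2% | 95.0–95.2% |
| 80% | 81.8–82.0% | 83.7–84.0% | 89.5–90.0% |

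The shift reaches the size of the 3-point half-width at roughly 20–30% borrowing.

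**The case against.** The strongest reply is that inflation is nowhere shown. No section says that pathology receives the NBI call. Section 4.2.2 puts it in the CRF, 5.1.1 starts data collection on a paper study form, and 4.4 places the predictions outside the medical record. This partial separation is real, but it does not reach the pathology request, so the gap stands while its consequence stays conditional.

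A reader might also infer more than the documents support:

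- *That CONECCT coding carries the test result into the reference (incorporation bias).* Figure 3 heads its columns with histological names, 2.1.1 equates IH and IS with histological types, and 4.2.2 calls the endoscopist's judgement a prediction of histology. Coding histology this way relabels a diagnosis. What is missing is the rule and the person applying it.
- *That several scalloped types have no class.* Sections 1.1 and 2.1.1 together place dysplastic sessile lesions in IS. Traditional scalloped adenoma is the one that stays arguable.
- *That the endoscopist codes the reference.* Section 5.1.1 says "All data are then entered into the eCRF by investigators", but the sentence goes on to coordinators and research nurses, and nothing says that whoever enters data interprets histology. Equally, nothing excludes the endoscopist who made the call.
- *That a 6-point shift swamps a ±3 interval.* That sets an IS bias against an IH+IS precision, and uses 80% where the plan assumes 90%.
- *That the damage could never be undone.* A blinded re-read of slides could address it, but none is planned.

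**Conclusion.** The point holds as an unstated safeguard with a known direction and an unknown size. The protocol does not blind pathologists to the endoscopic call, does not limit the specimen request, and does not say how or by whom histology becomes a CONECCT class. If the call reaches the reader or coder, sensitivity can only move up.

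On the assumed inputs, the rise in IS sensitivity is about 1–3 points at the plan's own 90% and about 2–6 points at 80%, inside the IS-only half-widths of about 7 and 10 points. For IH+IS versus IIA it is nil from IH/IS swaps. From scalloped/IIA borrowing it is about 1–2 points at 10% and 2–4 points at 20%. The borrowing shares, the 10% rate of IH called IS, and the specificity are not in the documents. The documents do not support saying that sensitivity *is* inflated. The gap is still worth closing, because a one-directional bias is not reflected in the confidence interval and prevention is cheap.

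**What to change.** In 4.2.2, state that the pathology request carries site, size and specimen number but no white-light, NBI or CONECCT call, and that pathologists read without access to the study form.

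In 2.2.2, have pathologists record the WHO histological type. Convert it with a mapping table fixed now, before any histology is linked to NBI results, and applied without sight of the NBI call. The table should give a stated class for traditional scalloped adenoma and list the other types explicitly. Waiting until database lock would be too late, because the mapping could then be chosen with both results in view.

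The cost is a short protocol change, a revised request form and a one-page table, with no extra reader, procedure or patients. There is a small downside: pathologists lose the endoscopist's impression. The request form also departs slightly from routine, which should be squared with the statements in 1.1 and 1.2.3 that usual management is unchanged.

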4.3 Study schedule

A one-hour training session on the NBI technique, based on clinical cases and commented image analysis for the characterization of colonic polyps, will be given by an expert endoscopist ([name]) at Nantes University Hospital and La Roche Sur Yon Hospital for all endoscopists taking part in the study. [name] is a graduate of the DIU "Endoscopie Diagnostique Avancée" (Advanced Diagnostic Endoscopy) and will be taking over the "colonic polyps" course of this training program. The training course will therefore not call on the services of an outside consultant, and will not require a specific budget.

The inclusion period is 48 months.

For patients :

- Inform patients about the study when they schedule their endoscopy examination in consultation or during hospitalization before the examination is performed.
- Each patient corresponding to the pre-inclusion criteria and having the presence of at least one polyp of less than 20 mm at colonoscopy will be included.
- Colonoscopy with white-light analysis and NBI for each patient.
- Polyp excised for standard histological analysis.

4.4 Identification of source data not included in the medical record

- Total number of polyps
- Total number of polyps <2cm
- Quality of colonic preparation according to Boston classification
- Suggested monitoring interval per patient after polyp analysis (by NBI and pathology)
- Endoscopist seniority

- Information on polyps (Paris classification, prediction in white light and NBI, CONECCT classification, image quality in white light and NBI, degree of certainty of prediction)

4.5 Rules for terminating a person's participation

4.5.1 Criteria for premature termination of a person's participation in research

For details of how and for how long people who left the study prematurely were followed up, please refer to the statistics section.

-Patient consent can be withdrawn at any time during the study, before results are published.

Right to object to data processing at any time during the study, before publication of results s.

4.5.2 Procedure for premature termination of a person's participation in research

Please refer to the statistics section for details of how to use data from people who left the study prematurely.

4.5.3 Criteria for discontinuing all or part of a research project (excluding biostatistical considerations)

Part or all of the study may be stopped permanently or temporarily by decision of the ANSM, the CPP or the study sponsor.

A written confirmation will be sent to the study coordinating investigator (specifying the reasons for premature termination) and to the principal investigator of each center, if applicable.

5. Data management and statistics

5.1 Study data collection and processing

5.1.1 Data collection

An electronic case report form (eCRF) will be created for each patient. All information required by the protocol must be provided in the eCRF. It must include the data needed to confirm compliance with the protocol and all the data required for statistical analysis, and to detect major deviations from the protocol.

Data will initially be collected on paper in an observation notebook, with a form for each polyp visualized, filled in by the endoscopist.

All data are then entered into the eCRF by investigators, clinical study coordinators (CECs) or clinical research nurses (CRNs).

The people responsible for filling in the eCRF (investigator, CEC, IRC, etc.) must be identified and their responsibilities defined in each center's table of delegated responsibilities (kept in the investigator binder).

5.1.2 Data coding

By signing this protocol, the principal investigator and all co-investigators undertake to keep confidential the identities of the patients who have participated in the study.

The transmission of a person's data for research purposes will therefore only be possible if a coding system is used; the presentation of research results must exclude any direct or indirect identification.

Patients (and polyps) will be identified in order of inclusion by a number automatically assigned by the Clinsight software (eCRF), then completed by the patient's initials.

This code will be the only information on the eCRF that can be used to link the eCRF to the patient.

The person in charge of the research is also required to code patient data on any documents in his/her possession (reports of imaging or biological examinations, etc.) which may be attached to the CRF.

A correspondence table will be set up at each center. This table will be kept in a secure place by the center's principal investigator, and will contain the patient code and nominative data, so that it can be traced back to the patient file in the event of missing or erroneous data. No clinical data will be collected in these correspondence tables.

5.1.3 Data processing

The collection of clinical data will be based on the creation of a clinical database and the creation of data entry masks in the image of the observation notebook, in compliance with the protocol and regulations currently in force.

The structure of the database and input screens will be approved by the research manager.

5.2 Statistics

Responsible for statistical analysis: [name] [name]

5.2.1 Description of planned statistical methods, including schedule of planned interim analyses and statistical justification of number of inclusions

Analysis of primary endpoint:

Sensitivity of the NBI technique to pathological findings for the characterization of colonic polyps (conventional adenomatous [CONECCT IIA] versus scalloped [CONECCT IS]) at colonoscopy will be calculated with its 95% confidence interval.

Secondary endpoints :

- The diagnostic performance (specificity, positive predictive value, negative predictive value, RV+, RV-, diagnostic accuracy (corresponding to the rate of correct responses)) of NBI for the characterization of colonic polyps (conventional adenomatous [CONECCT IIA] versus scalloped [CONECCT IS]) compared with standard histology will be estimated with their 95% confidence interval.

- The sensitivity and specificity of white light compared with standard histology results will be estimated with a 95% confidence interval and compared with those obtained by NBI using a McNemar test.

- If numbers permit, sensitivity analyses will be carried out:

- The sensitivity of NBI for the characterization of CONECCT IH and IS polyps versus CONECCT IIA will be estimated according to the certainty of the polyp characterization in NBI: strong or weak. These 2 sensitivities will be compared using a Chi2 test.

- The same analysis will be carried out on the seniority of the endoscopist: junior or senior.

- The same analysis will be performed according to polyp size: 1-5mm vs. 6-9mm vs. 10-20mm or 1-5mm vs. 6-20mm depending on numbers.

Number of subjects required :

Over 48 months, we plan to include 690 patients at Nantes University Hospital and the CHD de Vendée, with the aim of characterizing at least 690 polyps measuring less than 20 mm. About 50% of these will be CONECCT IIA polyps, 40% CONECCT IH and 10% CONECCT

IS. In addition, a majority of these polyps will be <5 mm in size (\approx 60%), \approx 30% between 6-9 mm and \approx 10% >10mm.

Assuming that 5% cannot be analyzed, and that the sensitivity of the NBI is 90%, we can estimate our sensitivity with a confidence interval of \pm 3%.

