5.2.2 Expected statistical significance

A p-value < 0.05 is considered statistically significant.

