5.2.5 Choosing the people to include in analyses

All polyps < 20mm characterized by NBI and standard histology of included patients will be analyzed.

6. Vigilance and management of undesirable events

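### Section 5.2.1 makes no allowance for polyps that share an endoscopist or a patient, so the primary 95% interval and the planned ±3% are likely too narrow, by an amount the documents do not fix

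*Combined protocol and SAP*

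**What the plan says.** - **Primary analysis (5.2.1).** NBI sensitivity against histology "at colonoscopy will be calculated with its 95% confidence interval". No interval method is named.
- **Precision (5.2.1).** With 5% of polyps not analysable and a sensitivity of 90%, "we can estimate our sensitivity with a confidence interval of" ±3%. The size is set by patients and polyps together: "we plan to include 690 patients at Nantes University Hospital and the CHD de Vendée, with the aim of characterizing at least 690 polyps".
- **Secondary comparisons (5.2.1).** White-light sensitivity and specificity are "compared with those obtained by NBI using a McNemar test". Subgroup sensitivities (certainty, seniority, polyp size) are compared by Chi2.
- **Unit of analysis (5.2.5).** "All polyps < 20mm characterized by NBI and standard histology of included patients will be analyzed".
- **Polyps per patient (3.1).** The expected mean is between 1 and 2. "A limit of 4 polyps per patient will be set for data collection".
- **Readers (4.2.2).** The endoscopist performing the examination makes the prediction for each polyp. The number of endoscopists is not stated.
- **Target.** The objective (2.1.1) takes IH and IS together against IIA. The endpoint (2.1.2) and the primary analysis (5.2.1) name IS.

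No section mentions clustering, a design effect, a robust variance, GEE, a mixed model or a cluster bootstrap.

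**The concern.** Two readings by the same endoscopist, or of two polyps in the same patient, are likely to be right or wrong together more often than two unrelated readings. A binomial interval over polyps ignores this and is too narrow under any positive correlation. The point matters here because section 2.1.1 asks about performance in a population of non-expert endoscopists. The participating readers are in effect a sample from that population, so differences between them belong in the interval. The plan itself allows that readers may differ, since endoscopist seniority is a secondary question, but a junior/senior comparison does not widen the primary interval.

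At stake are the coverage of the primary interval, the truth of the ±3% statement, and the validity of the p-values from the McNemar and Chi2 tests. The seniority comparison is the most exposed of these, because it contrasts groups of endoscopists.

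**Working it through.** **Inputs from the documents:** 690 polyps, 5% loss, sensitivity 0.90, mix of 50% IIA / 40% IH / 10% IS (all 5.2.1); mean of 1 to 2 polyps per patient, at most 4 (3.1).
**Assumed, because the documents are silent:** number of endoscopists J = 10, 20 or 40 with equal workloads; ICC among endoscopists of 0.01 to 0.05. At a sensitivity of 0.90 the between-endoscopist SD is √(0.09 × ICC), that is 3.0 points at 0.01 and 6.7 points at 0.05.

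**Step 1. Reproduce the ±3%.** Half-width = 1.96 × √(0.9 × 0.1 / n).

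- IH+IS: n = 690 × 0.95 × 0.50 = 327.75, giving ±3.25%.
- IS only: n = 690 × 0.95 × 0.10 = 65.55, giving ±7.26%.
- All analysable polyps: n = 655.5, giving ±2.30%.

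Among denominators that suit a sensitivity, only IH+IS rounds to ±3%. Taking IS+IIA (n = 393.3) gives ±2.96%, but IIA polyps do not belong in the denominator of a sensitivity for scalloped polyps. Either way the figure contains no design effect.

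**Step 2. Endoscopist clustering.** DE = 1 + (n/J − 1) × ICC. Clustered half-width = naive half-width × √DE. Coverage of the naive 95% interval = 2Φ(1.96/√DE) − 1.

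| J | ICC | IH+IS (328): DE | half-width | naive coverage | IS (66): DE | half-width | naive coverage |
|---|---|---|---|---|---|---|---|
| 10 | 0.01 | 1.32 | ±3.7% | 91% | 1.06 | ±7.5% | 94% |
| 10 | 0.05 | 2.59 | ±5.2% | 78% | 1.28 | ±8.2% | 92% |
| 20 | 0.01 | 1.15 | ±3.5% | 93% | 1.02 | ±7.3% | 95% |
| 20 | 0.02 | 1.31 | ±3.7% | 91% | 1.05 | ±7.4% | 94.5% |
| 20 | 0.05 | 1.77 | ±4.3% | 86% | 1.11 | ±7.7% | 94% |
| 40 | 0.01 | 1.07 | ±3.4% | 94% | 1.01 | ±7.3% | 95% |
| 40 | 0.05 | 1.36 | ±3.8% | 91% | 1.03 | ±7.4% | 95% |

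Worked line (J = 10, ICC 0.05, IH+IS): DE = 1 + (32.775 − 1) × 0.05 = 2.59; 3.25% × √2.59 = 5.2%; 1.96/√2.59 = 1.218, so coverage is 78%.

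Unequal workloads would raise these design effects.

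**Step 3. Patient clustering alone, IH+IS.** DE = 1 + (m* − 1) × ρ, where m* is the size-weighted mean number of target polyps per patient. Assumed: ρ of 0.1 to 0.5, mean of 1.5 or 2 polyps per patient, and target polyps either spread independently or concentrated in the same patients (m* from about 1.5 to 2.6).

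- 690 patients included: ±2.7% to ±3.2% at a mean of 1.5 (naive ±2.6%), and ±2.4% to ±3.1% at a mean of 2 (naive ±2.3%). The extra polyps roughly pay for the correlation.
- Recruitment stopped at 690 polyps from fewer patients: ±3.3% to ±4.4% (naive ±3.25%).

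**Step 4. Do more polyps cure the endoscopist effect?** With 690 patients at 1.5 polyps each (1035 polyps), n = 1035 × 0.95 × 0.5 = 491.6 and the naive half-width is ±2.7%. With 20 endoscopists and ICC 0.05, DE = 1 + (24.58 − 1) × 0.05 = 2.18, so the half-width is ±3.9% and naive coverage is 82%. The naive interval shrinks faster than the true one.

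**The case against.** - **The plan does not say that polyps are independent.** A reader might infer that it does. It names no interval method and is silent on correlation. Independence is an inference, though a reasonable one, from the polyp-level analysis set, the unmodified tests and the reproduced ±3%.
- **Endoscopist variation need not be the main source of uncertainty.** That stronger reading is tempting given the objective, but the documents do not support it. The between-endoscopist share of the variance is (n/J) × ICC / DE. For 328 polyps this is 25% at J = 20 and ICC 0.02, 46% at J = 20 and ICC 0.05, 30% at J = 40 and ICC 0.05, and 63% at J = 10 and ICC 0.05.
- **The readers may be fairly alike.** All receive the same training and must exceed 95% on a 30-image test (4.2.2). Section 1.1 speaks of a large population of endoscopists, which would favour a smaller design effect. This supports the low end of the range without settling it. A pass means 29 or 30 correct, the exact 95% lower limit for 29/30 is about 83%, and still images need not predict live readings.
- **Up to 4 polyps per patient sounds worse than it is.** At one polyp per patient there is no within-patient clustering, and with 690 patients step 3 leaves ±3% about met.
- **On the endpoint as worded (IS), clustering is a modest correction.** This stands. The choice between 66 and 328 polyps moves the precision far more than the clustering does.
- **No decision hangs on the interval.** The primary analysis is estimation, with no threshold or test, and the point estimate is the same under either interval method. This stands and limits the severity.

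**Conclusion.** The omission is real: as written, the primary interval, the ±3% and the planned tests make no allowance for correlated readings. How much too narrow the interval is cannot be read from the documents. With 10 to 40 endoscopists and ICC 0.01 to 0.05, both assumed, the IH+IS half-width is about ±3.4% to ±5.2% instead of ±3.25%, and naive coverage is about 94% to 78%. For IS it is about ±7.3% to ±8.2% instead of ±7.3%, with naive coverage of about 95% to 92%. The endoscopist level can matter more than the patient level.

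A reader might conclude that the ±3% should simply be replaced by something like ±3.5% to ±5%. That would be wrong for the endpoint as sections 2.1.2 and 5.2.1 define it, where precision is already ±7.3% before clustering. For the tests, the documents give no basis for a size. This should be fixed, with medium confidence on the size.

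**What to change.** 1. **Intervals (5.2.1).** Compute the primary and secondary confidence intervals with a cluster-robust method, clustered by endoscopist: for example GEE with a small-sample-corrected robust variance, or a cluster bootstrap. If each patient is examined by one endoscopist, this also covers the patient level. If there are only about 10 endoscopists, the small-sample correction is essential.
2. **Tests (5.2.1).** Use clustered versions of McNemar for NBI against white light and of Chi2 for certainty, seniority and polyp size.
3. **Data (4.4, 5.1).** Record a coded endoscopist identifier for each polyp in the eCRF. Section 4.4 lists seniority but no identifier, and section 5.1.2 describes numbering only for patients and polyps. The endoscopist completes the paper form, so the information exists at source.
4. **Precision (5.2.1).** Restate the ±3% with the expected number of endoscopists, an assumed design effect, and the denominator that matches the stated target. For illustration, 20 endoscopists and ICC 0.02 would give ±3.7% for IH+IS or ±7.4% for IS.

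The cost is revised analysis wording, one eCRF field, a little more analysis work and a less favourable stated precision. No extra patients or procedures are needed.
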